Worst toxicity CTCAE grade	Dose Modification	Recommended Clinical Management
Anemia		
Grade 3	
Hold study treatment.
 
Upon resolution to <math>\leq</math> Grade 2 or baseline within <math>\leq</math> 7 days, resume study treatment without dose modification.
 
If resolved in <math>></math> 7 days, reduce capmatinib <math>\downarrow</math> 1 dose level, and resume spartalizumab/placebo at same dose level.
	Treat per local/institutional guidelines
Grade 4	
Hold study treatment.
 
Upon resolution to <math>\leq</math> Grade 2 or baseline, reduce capmatinib <math>\downarrow</math> 1 dose level and resume spartalizumab/placebo at same dose level.
 
At second occurrence, permanently discontinue study treatment.
	Treat per local/institutional guidelines
Autoimmune hemolytic anemia, hemolytic uremic syndrome, or acquired hemophilia grade <math>\geq</math> 3	Discontinue spartalizumab/placebo	
Consult with specialist
 
Consider systemic corticosteroids and other therapies as appropriate (e.g. transfusion) per local institutional guidelines local institutional guidelines

Other adverse events		
Grade 1 or 2	
Maintain dose level, initiate supportive treatment as clinically indicated.
 
For any intolerable grade 2 (e.g. limiting instrumental ADL), consider omitting the dose until resolved to <math>\leq</math> grade 1, then then restart either at same dose or <math>\downarrow</math> 1 dose level.
	
Grade 3	Omit dose until resolved to $\leq$ grade 1, then $\downarrow$ 1 dose level	
Grade 4	Permanently discontinue capmatinib	
Note: All dose modifications should be based on the worst preceding toxicity.		

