Source Data/Document	Source data refers to the initial record, document, or primary location from where data comes. The data source can be a database, a dataset, a spreadsheet or even hard-coded data, such as paper or eSource
Stage of cancer	The extent of a cancer in the body. Staging is usually based on the size of the tumor, whether lymph nodes contain cancer, and whether the cancer has spread from the original site to other parts of the body
Start of the clinical trial	The start of the clinical trial is defined as the signature of the informed consent by the first subject
Study treatment	Any single drug or combination of drugs or intervention administered to the subject as part of the required study procedures
Study treatment discontinuation	When the subject permanently stops taking any of the study drug(s) prior to the defined study treatment completion date (if any) for any reason; may or may not also be the point/time of study discontinuation
Subject	A trial participant (can be a healthy volunteer or a patient depending on the study design)
Subject number	A unique number assigned to each subject upon signing the informed consent form. This number is the definitive, unique identifier for the subject and should be used to identify the subject throughout the study for all data collected, sample labels, etc.

Treatment arm/group	A treatment arm/group defines the dose and regimen or the combination, and may consist of 1 or more cohorts.
Variable	A measured value or assessed response that is determined from specific assessments and used in data analysis to evaluate the drug being tested in the study
Withdrawal of study consent (WoC)	Withdrawal of consent from the study occurs only when a subject does not want to participate in the study any longer and does not allow any further collection of personal data

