## 6 Treatment

### 6.1 Study treatment

The investigational drugs to be used in this study are capmatinib and spartalizumab, as described in [Table 6-1](#). The study treatment is defined as capmatinib plus spartalizumab or capmatinib plus placebo.

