## 6.2 Other treatment(s)

If a subject experiences an infusion reaction, he/she may receive pre-medication on subsequent dosing days. The pre-medication should be chosen per institutional practice at the discretion of the treating physician.

Acute allergic reactions should be treated as needed per institutional practice or the dose modification guideline ([Section 6.5.1](#)). In the event of anaphylactic/anaphylactoid reactions, this includes any therapy necessary to restore normal cardiopulmonary status. If a subject experiences a Grade  $\geq 3$  anaphylactic/anaphylactoid reaction, the subject will be discontinued from the study treatment.

The CTCAE category of “Infusion related reaction” should be used to describe study treatment related infusion reactions, unless the investigator considers another category, such as “Allergic reaction,” “Anaphylaxis,” or “Cytokine release syndrome” more appropriate in a specific situation.

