**Table 6-2 Dose reduction steps for capmatinib**

	Starting dose level 0	Dose level - 1	Dose level - 2
capmatinib	400 mg BID	300 mg BID	200 mg BID

Note: dose reduction should be based on the worst toxicity demonstrated at the last dose.

**Table 6-3 Dose modifications of capmatinib and spartalizumab/placebo and recommended clinical management for Adverse Events**

Worst toxicity CTCAE grade	Dose Modification	Recommended Clinical Management
Infusion related reaction or hypersensitivity reaction - Note: no action required with capmatinib treatment		
Grade 1	Decrease spartalizumab/placebo infusion rate until recovery from the symptoms.	Increase monitoring of vital signs as medically indicated until the subject is deemed medically stable in the opinion of the investigator.
Grade 2	Stop spartalizumab/placebo infusion immediately, and keep line open. If symptoms resolve, restart infusion at 50% of previous rate under continuous observation. If the AE recurs at the reinitiated slow rate of infusion, and despite oral pre-medication, then permanently discontinue spartalizumab/placebo treatment.	
 
1. Stop Infusion
 
2. Treat as per local institutional guidelines, which may include: i.v. fluids, antihistamines, NSAIDS, acetaminophen, narcotics, oxygen and corticosteroids as indicated
 
3. Increase monitoring of vital signs/pulse oximetry as medically indicated until patient is deemed medically stable
 
If symptoms resolve, the infusion may be restarted at 50% of the original infusion rate.
 
4. Premedicate patient ~ 1.5h prior to next infusion of spartalizumab/placebo with: 
 
• Diphenhydramine 50 mg po (or equivalent dose of antihistamine).
 
• Acetaminophen 500-1000 mg po (or equivalent dose of analgesic).
 
• Or as per local institutional guidelines
 
 
 

Grade $\geq 3$	Stop spartalizumab/placebo infusion immediately, and discontinue spartalizumab/placebo treatment permanently.	
 
1. Stop Infusion
 
2. Treat as per local institutional guidelines, which may include: iv fluids, antihistamines, NSAIDs, acetaminophen, narcotics, oxygen, corticosteroids, epinephrine
 
3. Close monitoring of vital signs, pulse oximetry and ECG as medically indicated until the patient is deemed medically stable
 
4. Hospitalization may be indicated.
 

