Guideline for significant deterioration in lung function: Decrease in spirometry and/or DLCO of 30% and/or O2 saturation ≤ 88% at rest on room air.

\*\* If bronchoscopy is performed, bronchoalveolar lavage (BAL) should be done where possible to exclude alveolar hemorrhage, opportunistic infections, cell count + determination lymphocyte CD4/8 count where possible.

\*\*\* Duration and dose of course of corticosteroids will vary according to circumstances but should be as limited as possible. Consider tapering dosage at end.

Worst toxicity CTCAE grade	Dose Modification	Recommended Clinical Management
ECG QTc-Interval prolonged		
Grade 3	
Hold study treatment.
 
Upon resolution to ≤ Grade 2 within ≤ 7 days, resume study treatment without dose modification,
 
If resolved in > 7 days, reduce capmatinib ↓ 1 dose level and resume spartalizumab/placebo at same dose level.
	
 
1. Perform an analysis of serum potassium, calcium, phosphorus, and magnesium, and if below lower limit of normal, correct with supplements to within normal limits.
 
2. Review concomitant medication usage for the potential to inhibit CYP3A4/5 and/or to prolong the QT-interval
 
3. Check compliance with correct dose and administration of capmatinib.
 
4. Repeat ECG within one hour of the first QTcF of ≥501 ms.
 
5. If QTcF remains ≥ 501 ms, repeat ECG as clinically indicated, but at least once daily until the QTcF returns to < 501 ms.
 
6. Repeat ECGs 7 days and 14 days (and then every 21 days) after dose resumption for all subjects who had therapy interrupted due to QTcF ≥ 501 ms.
 
 
If QTcF of ≥ 501 ms recurs, repeat ECGs as described above.
 
Notes: The investigator should contact the Novartis Medical Lead or designee regarding any questions that arise if a subject with QTcF prolongation should be maintained on study.

Grade 4	Discontinue study treatment.	As for Grade 3
Myocarditis		
Myocarditis grade ≥2 or other cardiac event grade ≥3	Mandatory: permanently discontinue study treatment	
Ensure adequate evaluation to confirm etiology and/or exclude other causes.
 
Initiate systemic corticosteroids (prednisone or equivalent) at a dose of 1-2 mg/kg/d
 
Consult with specialist; hospitalization as indicated

Worst toxicity CTCAE grade	Dose Modification	Recommended Clinical Management
Diarrhea/colitis		

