Grade 4 hyperglycemia or life-threatening complications	Hold spartalizumab/placebo until recovery to grade 1 or baseline  Permanently discontinue spartalizumab/placebo in case of recurring severe/life-threatening events not controlled by anti-glycemic therapy.	Initiate anti-glycemic therapy (i.e. insulin) as medically indicated Monitor glucose levels regularly until metabolic control is achieved Consider endocrinology consultation Evaluate for ketoacidosis as medically indicated Consider hospitalization (e.g. in case of ketoacidosis)
Encephalitis or aseptic meningitis - Note: no action required with capmatinib treatment	Discontinue spartalizumab/placebo	Rule out infectious or other causes of moderate to severe neurologic deterioration, and consult with specialist. If other etiologies are ruled out, administer corticosteroids at a dose of 1 to 2 mg/kg/day prednisone equivalents.
Guillain-Barre Syndrome, severe peripheral or autonomic neuropathy, or transverse myelitis - Note: no action required with capmatinib treatment	Discontinue spartalizumab/placebo	Hospitalization and consult with specialist
Other immune-related neuropathies (e.g. autoimmune neuropathy, demyelinating polyneuropathy, etc.) - Note: no action required with capmatinib treatment		
Grade 1	Continue study treatment	Provide symptomatic treatment evaluate/monitor adequately
Grade 2	Consider holding spartalizumab/placebo treatment until recovery to ≤ Grade 1 or baseline	Ensure adequate evaluation to confirm etiology or exclude other causes  Provide symptomatic treatment Systemic corticosteroids may be indicated Consider biopsy or additional tests for confirmation of diagnosis A specialist should be consulted
Grade 3	Hold spartalizumab/placebo until recovery to ≤ Grade 1 or baseline  May restart spartalizumab/placebo treatment at the same dose and schedule taking into account the risks and benefits	Initiate systemic corticosteroids (prednisone at a dose of 1-2 mg/kg/d or equivalent) and other therapies as appropriate Monitor closely and consult with a specialist

Worst toxicity CTCAE grade	Dose Modification	Recommended Clinical Management
Grade 4	Discontinue spartalizumab/placebo	Hospitalization and consult with specialist Initiate systemic corticosteroids (prednisone a dose of 1-2 mg/kg/d or equivalent) and other therapies as appropriate
Myasthenia gravis - Note: no action required with capmatinib treatment		

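### Table 6-3 calls for no capmatinib action after any hypersensitivity reaction, while Section 6.2 stops study treatment after Grade ≥3 anaphylaxis; for subjects on capmatinib alone the two rules do not agree

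*Protocol*

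**What the plan says.** Section 6.2 (Other treatment(s)) refers acute allergic reactions to institutional practice or to the dose modification guideline in Section 6.5.1. It then sets a fixed rule for the severe case: after a Grade ≥3 "anaphylactic/anaphylactoid reaction, the subject will be discontinued from the study treatment". Section 6.1 says what that term covers: "The study treatment is defined as capmatinib plus spartalizumab or capmatinib plus placebo".

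Table 6-3, which sits in Section 6.5.1, heads its row "Infusion related reaction or hypersensitivity reaction - Note: no action required with capmatinib treatment". The Grade ≥3 cell reads "Stop spartalizumab/placebo infusion immediately, and discontinue spartalizumab/placebo treatment permanently". The row makes no exception for anaphylaxis, and the table has no separate anaphylaxis row. The recommended management in that cell includes epinephrine and possible hospital admission, so severe reactions are within its scope.

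Section 9.1.1 lists what obliges the investigator to stop study treatment. For adverse events it points to Table 6-3 and does not mention Section 6.2. Section 6.7.2 records that spartalizumab has been stopped in all ongoing subjects. Nothing states whether Section 6.2 or the table prevails.

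**The concern.** Two places give different dosing instructions for capmatinib after the same event. What is at stake is safety conduct at the sites.

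The case that matters is the subject now on capmatinib alone. The row's instructions about slowing, stopping or restarting an infusion have nothing left to act on, so the only live dosing statement in it is the note about capmatinib. Taken literally, that note keeps capmatinib going after a severe hypersensitivity reaction that capmatinib itself may have caused. The protocol recognizes the hazard: exclusion criterion 2 in Section 5.2 bars patients with known hypersensitivity to capmatinib excipients.

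**Working it through.** The plan gives no figure to reproduce, so the check sets the texts side by side.

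**1. Does *study treatment* in Section 6.2 mean both drugs?** The protocol is not consistent.

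- For both drugs: the definition in Section 6.1; SAP Section 2.1.1.1, which defines study treatment as the combination; and Table 6-3, which keeps two separate orders. The myocarditis row says to "permanently discontinue study treatment", while the encephalitis row says only to "discontinue spartalizumab/placebo".
- For the antibody only: Section 6.2 gives a coding category that "should be used to describe study treatment related infusion reactions", and only spartalizumab/placebo is infused. Section 6.2.2.2 speaks of a next dose of study treatment in a steroid-tapering rule that can only concern the antibody, since capmatinib is taken twice daily. Section 6.5.2 attaches the 150-day window, which belongs to spartalizumab/placebo, to the last dose of study treatment.
- The glossary counts permanently stopping any one of the study drugs as study treatment discontinuation.

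**2. Subject on both drugs.** On the antibody reading, or through the glossary, stopping spartalizumab/placebo satisfies Section 6.2. That is also what the Grade ≥3 cell orders. The texts can be made to agree.

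**3. Subject on capmatinib alone.**

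| Reading of Section 6.2 | What Section 6.2 then orders | What the table note says |
|---|---|---|
| Both drugs (Section 6.1) | Stop capmatinib | No capmatinib action |
| Any one drug (glossary) | Stop capmatinib, the only drug left | No capmatinib action |
| Antibody only | Nothing, since no antibody is being given | No capmatinib action |

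The first two readings conflict with the row. The third agrees with it only by leaving the Section 6.2 sentence with no drug to stop, and then no event-specific rule stops capmatinib. None of the three gives an adequate instruction.

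**4. Which text does a site reach?** Section 9.1.1 points to Table 6-3, and Section 6.2 itself points to Section 6.5.1, so both routes lead to the row. Because hypersensitivity has its own row, a site has no evident reason to use the row for other adverse events. That row would not reproduce Section 6.2 either. It permanently stops capmatinib at Grade 4, but at Grade 3 it omits the dose and restarts one level lower.

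**5. Reach.**

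- Eight Table 6-3 entries carry the note: infusion/hypersensitivity, ocular, endocrinopathies, autoimmune diabetes, encephalitis or aseptic meningitis, the Guillain-Barre group, other immune-related neuropathies, and myasthenia gravis. Only for the first was another section found that orders an event-specific stop of study treatment.
- Amendment 1 (Study Update) reports 28 subjects treated with the combination and 3 in screening at the halt who then started capmatinib alone. 28 + 3 = 31, which matches the 31 treated in Section 4.1. On 06-Sep-2021, 19 were still on capmatinib.

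**The case against.** The strongest reply has four parts.

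*Both texts were written around infusions, and Section 6 often means the antibody when it says study treatment.* This stands for combination subjects. A reader might infer that Section 6.2 and Table 6-3 contradict each other for everyone in the trial. The usage in Sections 6.2, 6.2.2.2 and 6.5.2 and the glossary do not support that. It does not settle the capmatinib-alone case. The anaphylaxis sentence stands in the paragraph on acute allergic reactions and is not limited to infusions, and the table row adds hypersensitivity to infusion reactions.

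*The specific rule in Section 6.2 follows its general cross-reference, and saying that no action is required does not forbid stopping.* True: a site that stops capmatinib breaches nothing in the table, so the table cannot be said to prohibit a stop. The reverse is not safe. A site that follows the table alone and continues capmatinib departs from Section 6.2 on its defined meaning.

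*Amendment 1 says that only capmatinib guidance in Section 6.5.1 still applies, so the row is spent.* The note is the row's capmatinib guidance, so it is the part that survives.

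*Backstops exist.* Section 9.1.1 requires a stop wherever participation might put the subject at risk. Section 6.5.1 says that Grade 3 and 4 toxicities should in general lead to interruption. These limit the consequence considerably. However, the first rests on judgment, and the second calls for interruption rather than discontinuation and sits in the bullet on immune-related events.

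**Conclusion.** The inconsistency is real but minor, and it matters for subjects on capmatinib alone. It concerns one table row and one event type, in a group that numbered 19 on 06-Sep-2021. For subjects on both drugs the texts can be reconciled, and their infusions have ended. The conclusion rests on reading the table note as written, and on there being no precedence rule between Section 6.2 and the table; none was found.

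Three stronger inferences should be resisted.

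- A reader might want to attach a probability to the event. The documents give no rate for Grade ≥3 anaphylaxis, and hypersensitivity is not among the capmatinib adverse events of special interest in Section 10.2.1, so no figure should be quoted.
- A reader might describe the rule as covering only life-threatening reactions. Section 6.2 applies from Grade 3, which SAP Section 5.2 describes as generally severe; life-threatening corresponds to Grade 4.
- A reader might expect an effect on the results. No endpoint, analysis or scheduled assessment depends on this row.

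**What to change.** Make three wording changes.

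1. In the Table 6-3 row, limit the note so that capmatinib needs no action only when the reaction is attributed to the spartalizumab/placebo infusion.
2. Send any other hypersensitivity on capmatinib to the row for other adverse events.
3. State one rule for Grade ≥3 anaphylactic or anaphylactoid reactions, in the same words in Section 6.2 and in the row: permanently stop spartalizumab/placebo, and permanently stop capmatinib as well unless a cause other than capmatinib is established. The third change takes precedence over the second for these reactions.

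The cost is one table row and one sentence of Section 6.2, by amendment or preceded by a clarification letter to sites. No new assessments are needed. The downside is that some subjects will lose capmatinib when the cause stays uncertain. Section 6.2, on the Section 6.1 definition, already requires that. The proposed rule is milder, because it spares subjects in whom another cause is shown, for example contrast dye, an allergy that Section 6.2.2.2 foresees.

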## 6.5 Dose modification

### 6.5.1 Dose modification

For subjects who do not tolerate the protocol-specified dosing schedule, dose adjustments (reductions and/or interruptions) are permitted in order to allow subjects to continue the study treatment.

The following guidelines should be considered:

- Dose reductions are not permitted for spartalizumab/.
- Dose reductions are allowed for capmatinib and should follow the dose reduction steps described in [Table 6-2](#). For each subject, a maximum of two dose level modifications is allowed after which the subject must be discontinued. Dose reductions of capmatinib below 200 mg BID are not permitted.
- Dose re-escalation of capmatinib to the previous dose level is allowed only once, and if no AE leading to dose modification is observed after at least 1 cycle (4 weeks) of study treatment at the reduced dose.
- Dose interruptions due to toxicities are permitted for both spartalizumab and capmatinib. Dosing of capmatinib may resume once the adverse event has resolved, as described in [Table 6-3](#). All dose modifications, interruptions or discontinuations must be based on the worst preceding toxicity graded according to CTCAE v5.0 (<http://ctep.cancer.gov>).
- For clinical management of suspected immune-related events, reference to consensus management guidelines is recommended such as those provided in the National Comprehensive Cancer Network (NCCN) Guidelines for the Management of Immunotherapy-Related Toxicities (available at : [https://www.nccn.org/professionals/physician\\_gls/default.aspx#immunotherapy](https://www.nccn.org/professionals/physician_gls/default.aspx#immunotherapy)), the American Society for Clinical Oncology clinical practice guideline for Management of Immune-Related Adverse Events in Patients Treated With Immune Checkpoint Inhibitor Therapy ([Brahmer et al 2018](#)) or the European Society for Medical Oncology (ESMO) Clinical Practice Guidelines for Management of Toxicities from Immunotherapy ([Haanen et al 2017](#)). Note that in general, study treatment should be interrupted for grade 3 and 4 toxicities and for a subset of lower grade toxicities.
- Consider early referral to specialists with expertise in the diagnosis and management of immune-related AEs to thoroughly investigate events of uncertain etiology.
- Events not included in the study protocol or the reference guidance documents should be managed per institutional preference.

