- Overall, for adverse events of potential immune-related etiology (irAE) that do not recover to the extent required in the [Table 6-3](#) at a dose of immunosuppression of  $\leq 10$  mg/day prednisone or equivalent and/or requiring continuation of other immunosuppressive drugs within 12 weeks after initiation of immunosuppressive therapy, spartalizumab/placebo must be permanently discontinued.
- If, due to study drug related toxicity, a subject requires to interrupt capmatinib for  $> 3$  weeks, then the subject should be discontinued from study treatment. Exceptions to this requirement may be permitted following documented discussion with the Novartis medical monitor.
- Treatment continuation with spartalizumab alone is not permitted.

- All interruptions or change to study drug administration must be recorded on the Dose Administration Record eCRF.

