Grade 2 AST and/or ALT	
Hold study treatment.
 
Manage per institutional practice.
 
Upon resolution to ≤ Grade 1 or baseline, consider resuming study treatment without dose modification.
	
Monitor hepatic laboratory tests more frequently (every 2-3 days) until resolved to ≤ grade 1
 
Rule-out alternative causes (e.g. concomitant medications, infection, disease progression)
 
Consider prednisone (0.5-1 mg/kg/d) if liver tests worsen and/or significant symptoms

Grade 3 AST and/or ALT	
Hold capmatinib treatment.
 
Permanently discontinue spartalizumab/placebo
 
Upon resolution to ≤ Grade 1 or baseline within ≤ 7 days, resume capmatinib treatment without dose modification
 
If resolved in > 7 days, reduce capmatinib ↓ 1 dose level.
	
 
1. Monitor hepatic laboratory more frequently (every 2-3 days) until returned to ≤ grade 1.
 
2. Consult with hepatologist; consider hospitalization and liver biopsy to establish etiology
 
3. Initiate treatment with steroids (prednisone 1-2 mg/kg/d or IV equivalent)
 
4. Add prophylactic antibiotics for opportunistic infections as appropriate
 
5. Once symptoms/liver tests improve to Grade ≤1, taper steroids over at least 4 weeks
 
6. If no improvement or steroid refractory after 3 days, consider oral mycophenolate as per local treatment guidance
 
7. Infliximab is not recommended due to its potential for hepatotoxicity
 

Grade 4 AST and/or ALT	Mandatory: permanently discontinue study treatment.	As for Grade 3 toxicity above

Worst toxicity CTCAE grade	Dose Modification	Recommended Clinical Management
Isolated total bilirubin increased		
Grade 2	
Hold study treatment.
 
Upon resolution to <math>\leq</math> Grade 1 or baseline within <math>\leq</math> 7 days, resume study treatment without dose modification,
 
If resolved in <math>></math> 7 days, reduce capmatinib <math>\downarrow</math> 1 dose level and resume spartalizumab/placebo at same dose level.
	
Frequent monitoring of Liver Function Tests (LFTs), (every 2-3 days) until resolved to <math>\leq</math> grade 1
 
Rule-out alternative causes (e.g. concomitant medications, infection, disease progression)

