Grade 3	
Hold study treatment.
 
Upon resolution to <math>\leq</math> Grade 1 or baseline, reduce capmatinib <math>\downarrow</math> 1 dose level and resume spartalizumab/placebo at same dose level.
 
If resolved in <math>></math> 7 days, discontinue study treatment.
	
Frequent monitoring of LFTs, (every 2-3 days), until resolved to <math>\leq</math> grade 1. If resolved in <math>></math> 7 days, after discontinuing the subject from capmatinib permanently, the subject should be monitored weekly (including LFTs), or more frequently if clinically indicated, until total bilirubin have resolved to baseline or stabilization over 4 weeks

Grade 4	Mandatory: Discontinue study treatment.	
After permanently discontinuing the subject from study treatment, the subject should be monitored weekly (including LFTs), or more frequently if clinically indicated, until total bilirubin have resolved to <math>\leq</math> grade 1 or stabilization over 4 weeks.

Combined elevations of AST or ALT and Total Bilirubin		
Grade 2 AST and/or ALT with bilirubin $\geq$ Grade 2 (unless Gilbert's syndrome)	Mandatory: discontinue study treatment.	After permanently discontinuing the subject from study treatment, repeat LFTs as soon as possible, preferably within 48 hours from awareness of the abnormal results, then with weekly monitoring of LFTs, or more frequently if clinically indicated, until AST, ALT, or bilirubin have resolved to grade 1 or stabilization over 4 weeks
OR		
For participants with elevated baseline AST or ALT or total bilirubin value:		
[AST or ALT $>$ 3 x baseline]		
OR [AST or ALT $>$ 8.0 x ULN], whichever is lower, combined with [total bilirubin $>$ 2 x baseline AND $>$ 2.0 x ULN] without evidence of cholestasis or hemolysis		

Worst toxicity CTCAE grade	Dose Modification	Recommended Clinical Management
Amylase and/or lipase increased		
Grade 3	
Hold study treatment.
 
Upon resolution to <math>\leq</math> Grade 2 or baseline within <math>\leq</math> 14 days, resume study treatment without dose modification,
 
If resolved in <math>></math> 14 days, reduce capmatinib <math>\downarrow</math> 1 dose level and resume spartalizumab/placebo at same dose level.
	Perform CT scan or other imaging study to assess the pancreas, liver, and gallbladder must be performed within one week of the first occurrence of any $\geq$ Grade 3 of amylase and/or lipase elevation

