## 9 Study discontinuation and completion

### 9.1 Discontinuation

#### 9.1.1 Discontinuation of study treatment

Discontinuation of study treatment for a subject occurs when study treatment is stopped, and can be initiated by either the subject or the investigator.

The investigator must discontinue study treatment for a given subject if, he/she believes that continuation would negatively impact the subject's well-being. An end of treatment visit will be performed when subjects permanently discontinue the study treatment to which they were assigned at study entry.

Study treatment must be discontinued under the following circumstances:

- Disease progression per RECIST 1.1 as determined by investigator assessment (with or without confirmation by BIRC). In some circumstances subjects may be allowed to continue to receive study treatment beyond disease progression as per RECIST 1.1. These subjects will continue assessments as outlined in [Table 8-1b](#) and will complete the EOT visit only after permanent discontinuation of study treatment (see [Section 6.1.4](#))
- Subject/guardian decision
- Investigator decision
- Any situation in which study participation might result in a safety risk to the subject.
- Protocol deviation that results in a significant safety risk to the subject
- Adverse event requiring permanent discontinuation of study treatment (see [Table 6-3](#))
- Pregnancy
- Death

If discontinuation of study treatment occurs, the investigator should make a reasonable effort to understand the primary reason for the subject's premature discontinuation of study treatment and record this information.

Subjects who discontinue study treatment or who decide they do not wish to participate in the study further should NOT be considered withdrawn from the study UNLESS they withdraw their consent (see [Section 9.1.2](#)). **Where possible, they should return for the assessments indicated** in the assessment schedule. If they fail to return for these assessments for unknown

reasons, every effort (e.g. telephone, e-mail, letter) should be made to contact the subject/pre-designated contact as specified in [Section 9.1.3](#). This contact should preferably be done according to the study visit schedule.

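### Read literally, Table 6-3 stops capmatinib for Grade 2 AST/ALT with raised bilirubin but lets it restart after Grade 3 AST/ALT with the same bilirubin

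*Protocol*

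**What the plan says.** Table 6-3 handles liver tests in three blocks.

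- **AST and/or ALT increased.** At Grade 3, capmatinib is held and spartalizumab/placebo is stopped permanently. Then: "Upon resolution to ≤ Grade 1 or baseline within ≤ 7 days, resume capmatinib treatment without dose modification". If recovery takes longer than 7 days, capmatinib restarts one dose level lower. Grade 4 is a mandatory permanent stop. None of these rows mentions bilirubin.
- **Isolated total bilirubin increased.** At Grade 2, treatment is held; on recovery within 7 days the instruction is to "resume study treatment without dose modification", otherwise one level lower. Grade 3 allows a restart one level lower, or a stop if recovery takes more than 7 days. Grade 4 is a mandatory stop.
- **Combined elevations.** There is one action, mandatory discontinuation, with two alternative triggers. The first is "Grade 2 AST and/or ALT with bilirubin $\geq$ Grade 2", with an exception for Gilbert's syndrome. The second opens "For participants with elevated baseline AST or ALT or total bilirubin value" and has no upper limit on AST/ALT.

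The general guidance in Section 6.5.1 adds: "All dose modifications, interruptions or discontinuations must be based on the worst preceding toxicity graded according to CTCAE v5.0".

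**The concern.** The first trigger of the combined row names a single AST/ALT grade where a floor is needed. A subject with normal baseline and the more severe combination, Grade 3 AST/ALT with raised bilirubin, is not covered by that trigger, and the second trigger is confined to raised baselines. The Grade 3 AST/ALT row then governs and permits re-exposure to capmatinib. The milder combination forbids it.

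This is operative text. Amendment 1 revised the Table 6-3 criteria for reduction, interruption and re-initiation. The continuing subjects are on capmatinib, and Section 10.2.1 lists hepatotoxicity as a capmatinib adverse event of special interest. Re-exposure could also go further than the reduced dose: Section 6.5.1 allows one re-escalation to the previous level after at least one cycle without a dose-modifying adverse event, and it makes no hepatic exception.

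**Working it through.** There is no stated figure to reproduce. The check traces each case through the rows as printed.

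**Inputs.** Grade limits are from SAP Table 5-3, in multiples of ULN. AST/ALT: Grade 2 >3 to 5, Grade 3 >5 to 20, Grade 4 >20. Bilirubin: Grade 2 >1.5 to 3, Grade 3 >3 to 10, Grade 4 >10. The drug-induced liver injury criterion in Protocol Section 6.5.2.1 for a normal baseline is AST or ALT >3 x ULN with bilirubin >2 x ULN. Dose levels are from Table 6-2: 400, 300 and 200 mg BID.

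**Trace for a normal baseline without Gilbert's syndrome.**

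| ALT, bilirubin (x ULN) | Grades | Governing row, read literally | Action on capmatinib | Meets 6.5.2.1? |
|---|---|---|---|---|
| 4, 1.6 | 2, 2 | Combined | Mandatory stop | No |
| 5, 2.5 | 2, 2 | Combined | Mandatory stop | Yes |
| 5.1, 1.6 | 3, 2 | AST/ALT Grade 3 | Hold, may resume | No |
| 10, 2.5 | 3, 2 | AST/ALT Grade 3 | Hold, may resume | Yes |
| 20, 3.0 | 3, 2 | AST/ALT Grade 3 | Hold, may resume | Yes |
| 21, 2.5 | 4, 2 | AST/ALT Grade 4 | Mandatory stop | Yes |

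Resuming means the same dose if recovered within 7 days, or one level lower if later (for example 400 to 300 mg BID). ALT 4 with bilirubin 1.6 falls short of the Section 6.5.2.1 bilirubin threshold and must stop. ALT 10 with bilirubin 2.5 meets that section's criterion and may restart.

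**Applying the isolated-bilirubin rows as well, despite their heading.** At Grade 2 bilirubin nothing changes, because the restart terms are the same. At ALT 10 and bilirubin 5 (Grade 3) the result becomes one level lower, or a stop if recovery takes more than 7 days. At ALT 10 and bilirubin 11 (Grade 4) it becomes a stop. The gap is therefore firm at Grade 2 bilirubin and weaker above it.

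**Same on-study values, slightly raised baseline.** Take baseline ALT 1.2 and bilirubin 1.0 x ULN.

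- AST/ALT limit: the lower of 3 × 1.2 = 3.6 and 8.0, which is 3.6. ALT 10 exceeds it.
- Bilirubin limits: 2 × 1.0 = 2.0, and 2.0 x ULN. Bilirubin 2.5 exceeds both.

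The second trigger is met, so this subject must stop, absent cholestasis or hemolysis. The normal-baseline subject with identical values may restart.

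**Number exposed.** The Study Update in Amendment 1 gives 19 subjects on capmatinib at 06-Sep-2021. Section 1.1.1.2 gives treatment-related Grade 3/4 ALT increase of 4.8% and AST increase of 2.4% in the monotherapy study. If those rates applied here, Grade 3/4 events among 19 subjects would number about 0.048 × 19 = 0.9 (every AST case also an ALT case) to (0.048 + 0.024) × 19 = 1.4 (no overlap). That is before requiring concurrent bilirubin of at least Grade 2, a normal baseline and no Gilbert's syndrome, and before removing Grade 4. Residual spartalizumab effect could raise the rate. The documents do not give the joint frequency with bilirubin.

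**The case against.** The strongest reply is that no sensible site would read the row this way. The block is headed as covering combined elevations and has no higher step, so treating Grade 2 as a cap sends a combined case out of the only block written for it. The second trigger and Section 6.5.2.1 are both open-ended upwards. That makes the intended meaning almost certain, but no text states it. Elsewhere the table prints the sign when it means a floor, as in "Myocarditis grade ≥2 or other cardiac event grade ≥3". The worst-toxicity instruction also points a literal reader to the Grade 3 row.

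A second reply is that AST/ALT must pass back through Grade 2 on recovery, and a sample there with bilirubin still raised would meet the first trigger. This could narrow the gap. The protocol does not say that such a sample counts, and the outcome would then depend on when blood was drawn.

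A third reply is that safeguards exist:

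- Section 9.1.1 requires a stop in "Any situation in which study participation might result in a safety risk to the subject", and when the investigator believes continuation would harm the subject.
- A related capmatinib interruption beyond 3 weeks leads to this: "then the subject should be discontinued from study treatment. Exceptions to this requirement may be permitted following documented discussion".
- The Grade 3 row includes hepatology consultation.
- Section 6.5.2.1 requires work-up, and SAE reporting of cases confirmed on repeat testing with no alternative cause.

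These lower the risk. The first depends on judgement and names no liver threshold. The second allows exceptions and does not reach events that resolve sooner. The other two do not require a stop.

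Finally, the point turns on one character, and a sign lost when the table was converted to text cannot be wholly excluded. It is unlikely, because the sign on bilirubin in the same cell survived.

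**Conclusion.** The point holds. Followed as printed, the rule gives stop, may restart, stop across AST/ALT Grades 2, 3 and 4 for a subject with normal baseline, Grade 2 bilirubin and no Gilbert's syndrome. No other text makes the stop mandatory for the Grade 3 case. The conclusion assumes a literal reading of the row, and that a later Grade 2 sample does not trigger the stop retrospectively. It should be corrected because it is a live safety stopping rule. The practical reach is small: at most 19 subjects are under the rule, few if any are expected in the gap, and no endpoint or analysis is affected.

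**What to change.** In the first trigger of the combined row, put ≥ before Grade 2 for AST and/or ALT, and keep the Gilbert's exception. Add a sentence that the combined row takes precedence over the AST/ALT and isolated-bilirubin rows whenever either of its triggers is met. Subjects with Gilbert's syndrome who do not meet the combined row then stay under the AST/ALT rows. With this change the result is a stop at AST/ALT Grades 2, 3 and 4 alike.

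The cost is one symbol and one sentence, by amendment or site clarification letter. No new data or procedures are needed.
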